Protocol Non-CTIMP
Template Version 2.0 Review Date: December 2021

A cross-sectional study and a novel screening survey for radial artery assessment in surgical coronary revascularisation.

PROTOCOL

DATE 09/04/2024

CHIEF INVESTIGATOR – [name]

List Investigators – [name]
[name]
[name]

Investigation Sites: Royal Papworth Hospital; Royal Brompton Hospital

Principal Investigator: [name]

Protocol Identification Number: P00258

Date of Protocol: 20th November 2023

Review Date: 9th April 2024

Protocol Version Number: 4.0

Trial Sponsor: Royal Papworth Hospital (R&D Study Registration Number: P03105)

Contents

TRIAL OVERVIEW

1. Trial Overview	3
Primary Research Question	
Study Design	
Primary Outcome	
Secondary Outcome	
Rationale	
Schedule of Events	
2. Patient Recruitment	5
Study Population	
Inclusion Criteria	
Exclusion Criteria	
Recruitment Strategy	
3. Data Analysis and Document Retention	5
Sample Size	
Statistical Analysis	
4. Consent Process and Visit Schedule	6
Visit 1	
Follow-up Visit	
Informed Consent Procedure	
Table 1: Visit Schedule	
Table 2: Trial Specific Procedures versus Routine Procedures	
5. Follow up Visits and Travel Expenses	8
6. Data Collection and Auditing	9
Data Collection Form Completion	
Source Documentation	
Errors and Correcting	
Storage of Documents	
Retention of Documents	
Monitoring and Auditing	
7. Adverse and Serious Adverse Events	10
Recording & Reporting	
8. Amendments	11
Amendment log	

TRIAL OVERVIEW

1. Trial Overview

Primary Research Question

What factors influence the diagnostic accuracy of radial artery assessment in patients undergoing surgical coronary revascularisation?

Study Design

A multi-centre cross-sectional study to investigate the validity of radial artery assessment techniques in adults' people with ischaemic heart disease undergoing surgical coronary revascularisation with their radial artery being selected as an autologous graft conduit. Maximum expected duration of subject participation is 12 weeks.

Primary Outcome

Measure the sensitivity, specificity, negative and positive predictive values of the Modified Allen test (+/- pulse-oximetry), the Barbeau Test and ultrasonography examination.

Secondary Outcome(s)

- Measure the morphological and physiological quality of radial arteries through a validated structured questionnaire (Radial Artery Quality Evaluation Survey).

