- Measure the patients' finger movements, cold tolerance sensitivity and tactile/touch perception through an ordinal symptoms scale (Follow-up Radial Artery Harvesting Scale).

Rationale

The study will explore the accuracy of radial artery (RA) assessment in people with ischaemic heart disease (IHD) undergoing coronary artery bypass grafting (CABG). IHD affects 2.3 million people in the United Kingdom and is responsible for over 65,000 deaths per year. CABG results in the most effective therapeutic strategy for multi-vessel IHD while the RA is one of the preferred graft conduits. A comprehensive peri-operative RA assessment is essential to ensure disease-free RA segments are selected, precluding surgical complications such as hand ischaemia and graft failure. Whilst numerous screening tests are documented, their validity (diagnostic accuracy) is under debate. The literature is lacking evidence regarding the use of a standardised protocol for RA screening. The patients' experiences are seldom considered while surgical complications still occur. The expert opinion of professionals involved within the RA assessment and harvesting, generally the surgical care practitioners (SCP), is also not explored.

The intended research will provide an in-depth understanding of how assessment techniques inform RA harvesting in patients undergoing CABG, calibrating clinical decision and improving surgical practice. The research will uplift the SCP profession and address knowledge gaps, resulting in disciplinary and academic contributions.

Schedule of Events

Patients taking part in the study will receive an assessment of the arterial forearm circulation from their non-dominant upper extremity through the observations below.

- **Pre-operative observations.** Before surgery (in the ward environment after the patient is being admitted or whilst patient in the anaesthetic room) the forearm blood circulation is measured through the measures 1, 2, 3 and 4 to inform decision to surgically expose the RA.

1) Modified Allen Test (MAT). Instruct the patient to clench his/her wrist while the examiner occlude with three fingers the patient's ulnar and radial arteries; instruct the patient to unclench his/her wrist; release the ulnar artery. The MAT result is negative or positive considering in how long the palm flushes:

≤5 seconds negative MAT; good collateral hand circulation (suggesting harvestable radial artery)

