- **Post-operative observations.** Patients' finger movements, cold tolerance sensitivity and tactile/touch perception is measured through an ordinal symptoms scale (Follow-up Radial Artery Harvesting Scale) at post-operative day 2-5 and at follow-up appointment (3-6 weeks after surgery). Bilateral comparison between hands and forearms will be undertaken. Tactile perception is assessed through Semmes-Weinstein monofilaments (single touch). Cold sensitivity is assessed through the use of ice-pack.

The Follow-up Radial Artery Harvesting Scale was developed from a verbal rating scale (VRS) questionnaire documented in the literature and considered an accurate rating method for pinpointing the intensity of cold sensation. The VRS questionnaire was re-adapted to appreciate people's post-operative experience with their finger movements, cold sensitivity and tactile/touch perception of their forearm and will be used in this cross-sectional study. A Patient and Public Involvement and Engagement (PPIE) was undertaken on the Follow-up Radial Artery Harvesting Scale, gaining feedback from 9 adult cardiac patients from a clinical institution from the Greater London region. The PPIE resulted in improving readability and clarity of the questions and answers included in the scale.

2. Patient Recruitment Criteria

Study Population

- Sixty-nine patients from two cardio-thoracic clinical institutions from the East of England and Greater London regions.
- Cardiovascular sample group.
- Recruitment period: April 2024 – February 2025.
- End of study: 31st March 2025.
The end of study is the date of the completion of any follow-up monitoring and data collection described in the protocol.

Inclusion

- Diagnosis of ischaemic heart disease / coronary artery disease
- Age \geq 18 years
- Male and Female participants
- Elective or urgent coronary artery bypass graft (CABG) surgery and radial artery (RA) harvesting, with the RA being selected as one of the autologous graft conduits for the coronary revascularisation.

Exclusion

- Paediatric patients
- Emergency CABG
- Patients lacking capacity to consent
- Patients with limited understanding of English language and non-English-speaking patients requiring use of interpreters

Recruitment

- The planned recruitment target rate is:
 - April – August 2024: 34 patients
 - September 2024 – February 2025: 35 patients
- The recruitment rate has been calculated based on evidence from retrospective data.

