- *Recruitment review dates: June 2024, August 2024, November 2024, February 2024.*

Section 3. Sample Size and Data analysis

Sample Size

- A consecutive sampling method will be adopted for the recruitment of study participants. The minimum required number of participants to test and verify research hypotheses is sixty-nine patients (N=69). An adaptive trial design will be implemented: at quarterly assessment points the statistical power is assessed and the remaining sample size required is updated accordingly.

Statistical Analysis

- Sample size calculation was undertaken using G*Power software (version 3.1) using Chi-squared Test (χ^2) and adopting optimal effect size ($\omega=0.4$) and power (0.8).

4. Consent Process and Visit Schedule

Visit 1

- Potential participants will firstly be approached by clinicians within the healthcare team who is directly involved in delivering care and treatment to the patients. Clinicians will refer potential participants to the main investigator who will approach them for consenting purposes to take part in this study.

Follow-Up Visits

- Each patient will be assigned a study number; the study numbers will be allocated sequentially starting at 001.
- Visits should be scheduled and performed according to table 1.
- Trial specific procedures *versus* routine procedures are detailed in table 2 *if appropriate to the study*. The trial specific procedures will be performed after written informed consent has been obtained. The procedures that can be performed prior to consent being obtained are detailed in table 3 (*if appropriate*).

Table 1 Visit Schedule

Visit Number	Visit n	Visit n+1	Visit n+2
Time interval of Visit	week 0-3	week 0-3	week 4-12
Consent	X		
Pre-operative observation (Modified Allen Test +/- pulse-oximetry)		X	
Pre-operative observation (Barbeau Test)		X	
Pre-operative observation (Ultrasonography examination of forearm arteries)		X	
Intra-operative observation (oxygen saturation reading)		X	
Use of Questionnaire (Radial Artery Quality Evaluation Survey)		X	
Post-operative observation (Follow-up Radial Artery Harvesting Scale)			X

Table 2 Trial Specific Procedures *versus* Routine Procedures

Routine Investigations	Study Specific Procedures
Modified Allen Test +/- pulse-oximetry	Seeking Consent
Barbeau Test	Use of Questionnaire (Radial Artery Quality Evaluation Survey) currently under validation
Ultrasonography examination of forearm arteries	Use of Follow-up Radial Artery Harvesting Scale

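### Entry is tied to selection and harvest of the radial artery, which the studied tests help decide, so test-positive patients can be lost before enrolment and sensitivity and specificity biased

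*Combined protocol and SAP*

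**What the plan says.** Section 2 (Inclusion) asks for elective or urgent CABG and "radial artery (RA) harvesting, with the RA being selected as one of the autologous graft conduits". Section 1 (Study Design) repeats the restriction: adults "undergoing surgical coronary revascularisation with their radial artery being selected as an autologous graft conduit". Section 1 (Primary Outcome) is to "Measure the sensitivity, specificity, negative and positive predictive values of the Modified Allen test (+/- pulse-oximetry), the Barbeau Test and ultrasonography examination".

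Section 1 (Schedule of Events) says that before surgery "the forearm blood circulation is measured through the measures 1, 2, 3 and 4 to inform decision to surgically expose the RA". It makes exposure conditional on three ultrasound findings. Harvest is then decided during surgery, on a quality survey and a thumb oxygen saturation reading with the artery clamped.

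On sampling, Section 3 states: "A consecutive sampling method will be adopted for the recruitment of study participants". On referral, Section 4 (Visit 1) states: "Clinicians will refer potential participants to the main investigator who will approach them for consenting purposes". These clinicians belong to the treating team.

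On timing, Table 1 puts consent at the first visit and all the pre-operative tests at the second; both visits fall in weeks 0-3. Table 2 lists the tests as routine investigations. The rule on order covers only study procedures: "The trial specific procedures will be performed after written informed consent has been obtained".

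**The concern.** A diagnostic accuracy study should enrol people before the results of the tests under study can affect whether they enter. Here the entry condition is selection and harvesting of the radial artery, and the tests feed the decision to expose that artery. If a routine test is read as poor before referral, the treating team may not regard the artery as selected, and the patient never becomes eligible. Consecutive sampling would then mean consecutive among those who had passed.

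The word harvesting raises a second problem. A patient who consents, is tested and is then found not harvestable does not meet the criterion as written. No rule says that this patient stays in the study or counts towards the 69.

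Sensitivity and specificity are in the primary outcome, and both depend on the mix of test-positive and test-negative patients who get in. Patients who were never enrolled cannot be recovered at analysis.

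**Working it through.** **Plan's own figure.** The stated 69 reproduces as a chi-squared test with effect size 0.4 and power 0.80, if alpha 0.05 and 3 degrees of freedom are assumed (neither is stated); power at 69 is 0.8055. It has no bearing on who is selected.

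**Does the text allow filtering?**
- The tests act on the decision to use the artery: they are "measured through the measures 1, 2, 3 and 4 to inform decision to surgically expose the RA". Section 1 (Rationale) also treats assessment as the means of ensuring that disease-free segments are chosen, which puts selection after assessment.
- Table 1 orders consent before the study tests.
- Table 2 makes the same tests routine care, so the consent-first rule does not cover them. Section 4 also foresees some procedures before consent, listed in a Table 3 where appropriate. No such table is in the text, and I draw nothing from it either way.
- No section says when, or by what, the artery is selected. None requires a screening log.

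Filtering is therefore permitted, but not documented.

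**Size, if it happens.** The documents give no accuracy or prevalence figures, so every input here is assumed. Let r be the fraction of test-positive patients who are enrolled, with all test-negatives enrolled and entry depending only on this test.

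Apparent sensitivity = Se·r / (Se·r + 1 − Se)

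Apparent specificity = Sp / (Sp + (1 − Sp)·r)

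With Se = 0.70 and Sp = 0.85:

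| r | Apparent sensitivity | Apparent specificity |
|---|---|---|
| 1 | 0.70 | 0.85 |
| 0.5 | 0.35/0.65 = 0.538 | 0.85/0.925 = 0.919 |
| 0.2 | 0.14/0.44 = 0.318 | 0.85/0.88 = 0.966 |
| 0 | 0/0.30 = 0 | 0.85/0.85 = 1 |

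Other assumed true values at r = 0.5:
- Se 0.80, Sp 0.80: 0.40/0.60 = 0.667 and 0.80/0.90 = 0.889.
- Se 0.90, Sp 0.95: 0.45/0.55 = 0.818 and 0.95/0.975 = 0.974.

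In this model r cancels from PPV (which cannot be estimated at r = 0) and does not enter NPV, so neither is biased for the test that alone drives selection.

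**Numbers among the 69.** Assume 15% of arteries are truly not harvestable, with Se 0.70, Sp 0.85 and r = 0.2. The enrolled fraction is 0.021 + 0.0255 + 0.045 + 0.7225 = 0.814. The non-harvestable share is (0.021 + 0.045)/0.814 = 8.1%, or 5.6 of 69. Without selection it would be 0.15 × 69 = 10.35.

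**When a different test does the filtering.** Suppose test A (Se 0.70, Sp 0.90) removes all its positives, and test B has Se 0.80 and Sp 0.85. Let ρ be the correlation of the two results within true status.

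Apparent Se of B = [0.80 × 0.30 − ρ√(0.70 × 0.30 × 0.80 × 0.20)] / 0.30

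Apparent Sp of B = [0.90 × 0.85 + ρ√(0.90 × 0.10 × 0.85 × 0.15)] / 0.90

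ρ = 0 gives 0.800 and 0.850 (no bias); ρ = 0.3 gives 0.617 and 0.886; ρ = 0.5 gives 0.494 and 0.910.

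**If non-harvested patients were dropped.** The protocol names no reference standard. If harvestability were the target condition, no non-harvestable patient would remain. Sensitivity would be 0/0 and NPV would be TN/(TN + 0) = 100% by construction.

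**The case against.** A reader might infer that the protocol does remove test-positive patients before enrolment. The documents do not support that.

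- Table 1 schedules the study tests after consent, and Section 4 says that visits follow Table 1.
- The phrase about the artery being selected may describe only the surgical plan. The tests are said to inform exposure; no section says that they determine selection. A sequence of planned conduit, tests, exposure and then harvest fits the text, and on that reading test-positive patients can be enrolled.
- The Schedule of Events defines positive, not-harvestable results for people already taking part, which implies that such results are expected among participants.
- No section says that routine results are read before referral, or that non-harvested patients are dropped or replaced. The 0/0 case is sound arithmetic on a premise that the protocol does not state.
- The illustrated sizes rest wholly on assumed values, and a test that does not drive selection is biased only if it is correlated with one that does.

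All of this stands, and it limits the claim to a risk. It does not remove the risk. Table 1 governs study visits and does not bar a routine test beforehand, the harvesting requirement is in the criterion as written, and the protocol does not say that non-harvested patients are kept.

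**Conclusion.** The point holds as a risk of selection bias, with moderate confidence. Eligibility is worded in terms of a decision that the index tests inform and that is completed only in theatre. The protocol neither prevents routine results from deciding who is referred nor says that non-harvested patients remain.

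To the extent that filtering happens, sensitivity is understated and specificity overstated for the test that drives selection, and for tests correlated with it. With assumed true values of 70% and 85%, enrolling half of the test-positives gives 54% and 92%. The true size is unknown, because the documents give neither the accuracy of the tests nor the fraction lost.

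This is separate from the lack of intra-operative verification in arteries that are never exposed. That arises after enrolment, and repairing it would not bring back patients who never entered.

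**What to change.** 1. In Study Design and in the fourth inclusion criterion, describe the population as *elective or urgent CABG in which the radial artery is being considered as a graft conduit*.
2. State that eligibility and consent are settled before index-test results are used to decide on the radial artery, in line with the order in Table 1.
3. If a routine result was already known at consent, record this. Keep the patient, and run a sensitivity analysis without such patients.
4. State that every consented patient stays in the study and in the 69, whatever the test results and whether or not the artery is exposed or harvested.
5. Ask the referring team to pass on every patient being considered, and keep a log of those considered but not enrolled, with reasons.

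No exposure or harvest rule changes. The cost is a protocol amendment and a simple log, and consent may have to come earlier in the pathway. Slightly fewer of the 69 will contribute to the follow-up scale, because some will have no harvest. Arteries that are not exposed will still lack intra-operative verification and need their own analysis rule.

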>5 seconds positive MAT; poor collateral hand circulation (suggesting not-harvestable radial artery)

2) Pulse-oximetry guided MAT. A pulse-oximetry probe is positioned on the patient's index finger; both radial and ulnar arteries are occluded by the examiner (with three fingers) until flattening of pulse waveform is obtained. Pressure on the ulnar artery is released and the result of the assessment is calculated considering in how long the pulse waveform returns to baseline:

≤5 seconds negative result (suggesting harvestable radial artery)
>5 seconds positive result (suggesting not harvestable radial artery)

3) Barbeau Test. A pulse-oximetry probe is positioned on the thumb; the radial artery is then compressed by the examiner, and the pulse waveform is analysed for up to 120 seconds, providing four patterns of ulnar-palmar patency:

- a. No damping of the pulse tracing immediately after compression (suggesting harvestable radial artery)
- b. Damping of the pulse tracing (suggesting harvestable radial artery)
- c. Loss of the pulse tracing, followed by recovery within 120 sec (suggesting harvestable radial artery)
- d. Loss of the pulse tracing, without recovery within 120 sec (suggesting not harvestable radial artery).

4) Ultrasonography examination of the forearm arteries. The radial artery is surgically exposed (negative result) when the following apply:

- a. ulnar artery inner diameter ≥2 mm
- b. radial artery inner diameter ≥2 mm
- c. absence of radial artery intraluminal calcifications and plaques.

- **Intra-operative observations.** The radial artery is surgically harvested when the following apply:

A) The radial artery morphological and physiological characteristics (diameter, calcifications, presence of pulsatile flow), quality of harvesting technique and surgical accessibility are considered satisfactory, good or optimal. Measures are taken through a structured questionnaire (Radial Artery Quality Evaluation Survey) currently being validated through a Delphi study.

B) Oxygen saturation reading (SpO_2) from the thumb through pulse-oximetry remains at 95% or above when an occlusive atraumatic clamp is applied on the mobilised RA.

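### The 0.8 power behind N=69 belongs to an unnamed chi-squared test and says nothing about the precision of the primary outcome (sensitivity, specificity, PPV, NPV)

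*Combined protocol and SAP*

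**What the plan says.** The protocol's research question (Section 1, Primary Research Question) is: "What factors influence the diagnostic accuracy of radial artery assessment in patients undergoing surgical coronary revascularisation". The primary outcome (Section 1, Primary Outcome) is one of measurement: "Measure the sensitivity, specificity, negative and positive predictive values of the Modified Allen test (+/- pulse-oximetry), the Barbeau Test and ultrasonography examination".

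Section 3 (Sample Size) states: "The minimum required number of participants to test and verify research hypotheses is sixty-nine patients (N=69". The basis is given under Statistical Analysis: "Sample size calculation was undertaken using G*Power software (version 3.1) using Chi-squared Test", with w = 0.4 and power 0.8. That subsection contains nothing else. Section 3 also plans an adaptive step: "at quarterly assessment points the statistical power is assessed and the remaining sample size required is updated accordingly".

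Nowhere does the protocol give alpha, degrees of freedom, the table to be tested, the hypothesis, an expected prevalence of non-harvestable arteries, expected accuracy, a target interval width, or the reference result against which the tests are judged.

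Three further places matter:

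- Section 1, Schedule of Events, pre-operative observations: "the forearm blood circulation is measured through the measures 1, 2, 3 and 4 to inform decision to surgically expose the RA".
- The same section, under ultrasonography: "The radial artery is surgically exposed (negative result) when the following apply". The intra-operative criteria then follow: "The radial artery is surgically harvested when the following apply".
- Section 2, Inclusion: patients enter with the radial artery already selected as a conduit.

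**The concern.** A reader of Section 3 will take 0.8 as the trial's power for its primary outcome. It is the power of a test of association. The primary outcome is a set of proportions to be estimated, and no hypothesis about them is stated.

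The precision of sensitivity and specificity is set by the numbers of verified non-harvestable and harvestable arteries. The precision of PPV and NPV is set by the numbers of verified test-positive and test-negative arteries. Without these, nobody can tell in advance whether 69 patients can separate a poor screening test from a good one. The quarterly update could also change the sample size on a quantity unrelated to the primary outcome.

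A second issue concerns which arteries get a reference result at all. If that result can be seen only once the artery is exposed, and exposure follows only a negative ultrasound, then some of the primary measures for ultrasound cannot be estimated at any sample size.

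**Working it through.** **Step 1: reproduce 69.** Inputs from Section 3: w = 0.4, power 0.8. Assumed: alpha 0.05. Power is P[χ²(df, noncentrality N·w²) > critical value], and w² = 0.16.

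| df | Smallest N for power 0.8 | Power at N = 69 |
|---|---|---|
| 1 | 50 | 0.9135 |
| 2 | 61 | 0.8540 |
| 3 | 69 | 0.8055 |
| 4 | 75 | 0.7639 |

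At df = 3 the noncentrality is 69 × 0.16 = 11.04; power is 0.7991 at N = 68 and 0.8055 at N = 69. So 69 is exact for df = 3 and alpha 0.05, both inferred. Two other settings come close without matching: df = 1 at alpha 0.0125, and df = 6 at alpha 0.10, each needing 70. A single 2×2 table of test against reference (df = 1, alpha 0.05) would need 50.

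**Step 2: precision of the primary outcome at N = 69.** The protocol gives no prevalence or expected accuracy, so these are assumptions: prevalence of non-harvestable arteries 10 to 50%, sensitivity 0.8, specificity 0.9, and all 69 arteries verified (the best case). The expected width is the Clopper-Pearson 95% width averaged over the binomial distribution of the counts. For PPV and NPV the average is over true and false positives jointly.

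| Prevalence | Non-harvestable / harvestable | Example sensitivity (exact 95% CI) | Sensitivity width | Specificity width | PPV width | NPV width |
|---|---|---|---|---|---|---|
| 10% | 7 / 62 | 6/7 (42.1–99.6%) | 58.8 | 16.1 | 57.7 | 10.0 |
| 20% | 14 / 55 | 11/14 (49.2–95.3%) | 43.4 | 17.2 | 46.2 | 13.8 |
| 30% | 21 / 48 | 17/21 (58.1–94.6%) | 35.9 | 18.4 | 36.6 | 17.7 |
| 50% | 34 / 35 | 27/34 (62.1–91.3%) | 28.3 | 21.7 | 24.4 | 25.7 |

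Widths are in percentage points. In the same order of prevalence, the sensitivity width is 64, 48, 40 and 32 if true sensitivity is 0.7, and 51, 35, 28 and 22 if it is 0.9.

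The inclusion criterion may put prevalence at or below the low end. At 5% there are about 3 non-harvestable arteries. The exact widths for 0, 1, 2 and 3 detected out of 3 are 70.8, 89.7, 89.7 and 70.8 points. At sensitivity 0.8 the expected width is 0.008 × 70.8 + 0.096 × 89.7 + 0.384 × 89.7 + 0.512 × 70.8 ≈ 80 points.

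**Step 3: if only ultrasound-negative arteries are verified.** Ultrasound true positives (TP) and false positives (FP) are then both zero among verified arteries. With FN and TN the false and true negatives:

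- Sensitivity = TP/(TP + FN) = 0/FN, which is 0 whatever the true value (undefined if FN = 0).
- Specificity = TN/(TN + FP) = TN/TN, which is 1 whatever the true value.
- PPV = TP/(TP + FP) = 0/0, undefined.
- NPV = TN/(TN + FN), which can be estimated.

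With ultrasound at 0.8/0.9 (assumed), expected verified arteries are FN + TN:

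| Prevalence | FN | TN | Verified of 69 |
|---|---|---|---|
| 10% | 7 × 0.2 = 1.4 | 62 × 0.9 = 55.8 | 57.2 |
| 20% | 14 × 0.2 = 2.8 | 55 × 0.9 = 49.5 | 52.3 |
| 30% | 21 × 0.2 = 4.2 | 48 × 0.9 = 43.2 | 47.4 |
| 50% | 34 × 0.2 = 6.8 | 35 × 0.9 = 31.5 | 38.3 |

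The sensitivity of any other test would rest on the FN column, for example 2/3 (9–99%), 3/4 (19–99%) or 6/7 (42–100%).

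**The case against.** - **The chi-squared test may properly serve the question about factors.** Three degrees of freedom would suit a four-category classification, such as the four Barbeau patterns, against a binary result. This is possible, but Section 3 does not say so, and the primary outcome would still have no planning basis.
- **The figure is arithmetically right.** This stands. A reader might infer that 69 is a miscalculation; it is not. The missing df and alpha are a reporting gap.
- **A small descriptive study needs no power, and exact intervals in the results will show the imprecision.** This is fair as far as it goes. But the protocol itself claims a minimum N and a power, and readers of the plan need to know what these cover before the data arrive.
- **The prevalence range is invented.** It is assumed, because the protocol gives none. The widths are illustrations and do not predict the trial's result. A lower prevalence, which the inclusion criterion makes credible, makes sensitivity less precise still.
- **Verification may not be restricted to negative ultrasounds.** This stands as a limit on the point. The ultrasound text says when the artery is exposed but not that it is exposed only then, and the pre-operative text has all four measures informing the decision. The conclusion about ultrasound is therefore conditional.

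**Conclusion.** The point holds. The 0.8 power and the minimum of 69 come from an unnamed test of association and do not describe how precisely the primary outcome will be estimated. In the best case of full verification with sensitivity 0.8, the expected interval for sensitivity runs from about 59 points wide at 10% prevalence to 28 points at 50%. These widths rest on assumed prevalence and accuracy; that no precision basis is given does not.

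The ultrasound consequence rests on two further conditions: an intra- or post-operative reference result, and exposure only after a negative ultrasound. The second is the natural reading of the ultrasound criteria but is not settled by the text. If both hold, three of the four ultrasound measures are lost and the other tests are assessed in a selected subset.

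Two stronger readings are not supported. One is that the trial needs a particular larger N: the protocol gives no prevalence, expected accuracy or target width from which to derive one. The other is that ultrasound sensitivity certainly cannot be estimated: the reference result is not named and the exposure rule is ambiguous.

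**What to change.** The planned 69 is unchanged.

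1. In Section 3, name the hypothesis behind the chi-squared calculation, with its table, df and alpha. State that the 0.8 power applies to that hypothesis only and does not size the accuracy measures.
2. Name the reference result. Give the expected exact 95% interval widths for sensitivity, specificity, PPV and NPV at N = 69, over a stated prevalence range that includes values below 10%, counting only verified arteries.
3. At each quarterly review, report the verified non-harvestable and harvestable counts and, for each test, the verified positive and negative counts, with the resulting widths. State which quantity drives the planned sample-size update and how it is computed.
4. Reconcile the pre-operative and ultrasonography text in Section 1 on when the artery is exposed. If verification follows only a negative ultrasound, declare ultrasound sensitivity, specificity and PPV not estimable, report ultrasound NPV only, and report the other tests' accuracy as conditional on a negative ultrasound.

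The cost is wording in Sections 1 and 3, a reference result recorded for each artery, and a few extra counts at reviews already planned. The stated figures will look less favourable, and up to three ultrasound measures may leave the primary outcome.

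### The chi-squared calculation behind N=69 assumes independent observations and gives neither power nor precision for the primary accuracy measures, which come from tests done on the same arm of each patient

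*Combined protocol and SAP*

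**What the plan says.** Section 1 (Trial Overview, Primary Outcome) sets the aim: "Measure the sensitivity, specificity, negative and positive predictive values of the Modified Allen test (+/- pulse-oximetry), the Barbeau Test and ultrasonography examination". It writes out no hypothesis and no comparison between tests.

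Under Schedule of Events, each patient has an "assessment of the arterial forearm circulation from their non-dominant upper extremity through the observations below", and before surgery "the forearm blood circulation is measured through the measures 1, 2, 3 and 4". These are the Modified Allen test, its pulse-oximetry version, the Barbeau test and ultrasonography. Each ends in a call for or against harvesting, so every patient supplies several binary results from one limb.

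In Section 3, the Statistical Analysis heading holds one sentence: "Sample size calculation was undertaken using G*Power software (version 3.1) using Chi-squared Test", "adopting optimal effect size ($\omega=0.4$) and power (0.8". Under Sample Size: "The minimum required number of participants to test and verify research hypotheses is sixty-nine patients (N=69". The same paragraph says that power is reassessed each quarter and the remaining sample size updated. The document gives no alpha, degrees of freedom, hypothesis, confidence-interval method, paired method or analysis model.

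**The concern.** A study of diagnostic accuracy needs a sample size that says how precisely sensitivity and specificity will be estimated or, if tests are compared, how well a paired difference will be detected. The plan offers a chi-squared power figure instead. The effect size w carries no information about the number of reference-positive or reference-negative arteries, or about agreement between tests on the same arm.

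Two things are at stake. First, the stated power of 0.8 does not describe the primary outcome, yet it is the only stated basis for the quarterly power review. Second, if the one named test is carried into the analysis to compare techniques, it ignores the pairing. Real differences would then be missed, and the advantage of each patient acting as their own control would be lost.

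**Working it through.** **1. Reproducing 69.** Inputs from Section 3: w=0.4, power 0.8. Alpha and df are not stated; alpha 0.05 is assumed. The test statistic follows a noncentral chi-squared distribution with noncentrality N × w² = N × 0.16. The smallest N with power of at least 0.80 is:

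| df | N | power |
|---|---|---|
| 1 | 50 | 0.807 |
| 2 | 61 | 0.805 |
| 3 | 69 | 0.806 |
| 4 | 75 | 0.802 |

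At 3 df, 69 × 0.16 = 11.04 and the critical value is 7.815. With N=68 the power is 0.799. So 69 is arithmetically right for 3 df.

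**2. What 3 df could mean.** Two readings fit.
- Four tests by two results: (4−1) × (2−1) = 3. The calculation would then count 69 independent entries, about 69/4 ≈ 17 per test. The design gives up to 69 × 4 = 276 correlated results.
- One four-level variable, such as the four Barbeau patterns, against harvestable or not, with one row per patient. This also has 3 df and respects independence, but it tests association. It neither estimates nor compares sensitivity or specificity.

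On neither reading does the figure of 0.8 apply to the primary outcome.

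**3. If chi-squared were used across the tests.** All inputs here are assumptions: 60 reference-negative arteries, four tests, results linked by a shared latent normal factor, 20,000 simulated studies per cell, nominal alpha 0.05. Power uses specificities 0.80, 0.85, 0.90 and 0.95. The false-positive rate uses 0.85 for all four.

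| Latent correlation | Chi-squared power | Cochran's Q power | Chi-squared false-positive rate |
|---|---|---|---|
| 0.3 | 0.56 | 0.65 | 0.027 |
| 0.5 | 0.55 | 0.72 | 0.014 |
| 0.7 | 0.51 | 0.81 | 0.004 |

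Cochran's Q keeps a false-positive rate of about 0.045. At zero correlation the two tests agree, with power 0.57 to 0.59 for both in repeat runs. The correlations are latent; with specificity 0.85 they correspond to a phi between test results of about 0.15, 0.28 and 0.44.

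A second setting uses all 69 patients and assumed positivity rates (10,000 runs). With rates of 10/15/20/30% and phi 0.26, power is 0.76 for chi-squared and 0.88 for Cochran's Q. With rates of 10/20/20/25% and phi 0.26, it is 0.42 and 0.63.

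**4. What 69 patients give in precision.** The plan gives no expected split by reference result. Take 60 reference-negative as above, leaving 69 − 60 = 9 reference-positive. The Wilson 95% interval has centre (p + z²/2n)/(1 + z²/n) and half-width z/(1 + z²/n) × √(p(1−p)/n + z²/4n²), with z = 1.96.
- Specificity 51/60 = 0.85: centre 0.829, half-width 0.090, interval 0.74 to 0.92.
- Sensitivity 7/9 = 0.78: centre 0.695, half-width 0.242, interval 0.45 to 0.94.

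The chi-squared calculation conveys nothing of this contrast.

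**The case against.** The strongest reply is that chi-squared appears only in a sample size sentence. The protocol never says that it will compare the tests, and the primary outcome is to measure each test's accuracy. A reader might infer from 3 df that the authors planned a four-tests-by-two-results table with pairing ignored. The documents do not support that: the Barbeau patterns give the same df with one row per patient, and equating N with 69 patients fits that reading better than about 17 entries per test. This stands, and the point is limited accordingly.

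A reader might also infer that false claims of superiority are likely. They are not: under positive correlation the unpaired test rejects too rarely, so the cost is missed differences. Nor is 69 a miscalculation, since it reproduces exactly.

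The size of the loss rests on assumed rates and correlations, and at zero correlation there is none. Some positive correlation is plausible, because the two Allen variants share the same occlusion, ulnar release and 5-second cut-off, and the Barbeau test also assesses ulnar-palmar patency. The simulation treats the four tests alike, whereas Schedule of Events ties surgical exposure to a negative ultrasound result. That may restrict which arteries have a reference result, so the figures are illustrative only. Table 1 also lists "Pre-operative observation (Modified Allen Test +/- pulse-oximetry", so not every patient need have that version; the remaining tests are still paired.

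What the reply does not answer is that neither reading of the calculation serves the primary outcome.

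**Conclusion.** The concern holds in a limited form. The one inferential method and power figure in the plan assume independent observations and give neither power nor precision for sensitivity, specificity, PPV or NPV. This follows from the text and does not depend on the simulation.

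The loss from an unpaired comparison is conditional on chi-squared being used for that purpose, which the plan does not state. Under the assumptions shown, the shortfall in power is about 0.09 at latent correlation 0.3 (0.65 − 0.56) and 0.30 at 0.7 (0.81 − 0.51). The direction holds for positive correlation; the size depends on unstated rates. The plan should be changed, because the remedy is cheap and the primary outcome currently has no stated analysis.

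**What to change.** Rewrite the Statistical Analysis section as follows.

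- **Primary analysis:** each test's sensitivity, specificity, PPV and NPV against the stated reference result, with exact or Wilson 95% confidence intervals.
- **Any between-test comparison:** paired. Compare sensitivity within reference-positive patients and specificity within reference-negative patients, by Cochran's Q followed by exact McNemar tests. For predictive values use a paired method such as GEE with robust variance. State the hypotheses and alpha.
- **Sample size:** replace the chi-squared power statement with the interval width that 69 patients give for the expected numbers of reference-positive and reference-negative arteries. Base the quarterly review on the same quantity.

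The cost is a short section of text, with no extra patients, data or staff. The downside is a justification that looks less favourable: if few arteries are reference-positive, sensitivity will be visibly imprecise.
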